#### 7.1.2.6.2 Tumor Imaging During Trial

The first imaging assessment should be performed at approximately **100 days after completion of radiation therapy**. For the purposes of this study, this is considered the "treatment end" imaging study. This will be approximately day 150 from the first dose of radiation. Due to treatment variations and delays, this may be delayed by up to 14 days.

Follow-up imaging will occur at scheduled intervals outlined on the Flow Chart. At 1 year following completion of the study treatment PET/CT imaging is not required, but is suggested

and is allowed so long as diagnostic quality CT images are included. Diagnostic quality imaging of the primary tumor site (CT scan of the neck) should be performed annually thereafter for up to 5 years. Images will be reviewed by the central radiologist at the end of the study to confirm disease response for purposes of study evaluation.

Additional imaging should be performed per clinical guidelines and is not required the study. Patients with clinical signs and symptoms of progression should have follow-up imaging as deemed clinically necessary. If this occurs during the study period, it should be reported to the study.

During the follow up period, if an instance occurs where the participants insurance will not approve a diagnostic CT scan a clinical evaluation will be used. No protocol deviation is needed but the insurance denial must be documented on the tumor assessment source documents.

# 7.1.2.6.3 Assessment of Disease – RECIST 1.1, irRECIST 1.1, PET Response, Salvage Surgery

#### 7.1.2.6.3.1 RECIST 1.1

RECIST 1.1 will be applied by the individual sites for assessment of tumor response. Sites should also assess tumor response and progression per modified RECIST 1.1 and this data will be collected in the clinical database. Site assessment of tumor response and progression will be used for all patient decision making in the trial. See Section 11.3 and 11.4.

#### 7.1.2.6.3.2 irRECIST 1.1

irRECIST 1.1 will not be used in this study. Any patient with documented progression, partial response, or stable disease on post-treatment imaging will undergo salvage surgical procedures to confirm pathologic response (see Section 7.1.2.7.3.3).

#### 7.1.2.6.3.3 PET Response (Hopkins Criteria)

Hopkins Criteria will be used to assess PET response when PET imaging is utilized. This is outlined in section 11.5. PET is not required, but is allowable to assist in determine the primary efficacy outcome when RECIST 1.1 data is considered not clinically representative of response. Patients without a RECIST 1.1 CR, but with a Hopkins Criteria negative predictive value (NPV) (See section 11.5) can forgo salvage surgery and be considered as having a CR in terms of the primary efficacy measure.

#### 7.1.2.6.3.4 Salvage Surgery

Patients with residual disease considered resectable after all their planned therapy is completed may undergo a salvage surgical procedure, if that procedure is conceived as potentially curative.

PET imaging can be used to guide post treatment surgical need. The preference of the study would be to recommend no further therapy for any PET tumor avidity (CMR). However, this is not a requirement and will be left up to the discretion of the treating surgical oncologist.

Patients achieving a complete response who had advanced (N2 or greater) neck disease at presentation should be considered for an elective neck dissection after completion of all of their planned therapy if the post therapy imaging or clinical exam indicates persistent disease, despite RECIST 1.1 response. The nature of the neck dissection will be at the discretion of the treating head and neck surgeon.

Pathologic response to therapy will be evaluated following surgery. Pathological complete response (pCR) is defined as the absence of residual invasive and in situ cancer on hematoxylin and eosin evaluation of the completely resected sites of residual disease. Subjects who have a pathologic CR, but do not have a RECIST 1.1 CR will be included in the final efficacy analysis. This analysis will include the composite outcome of patients with RECIST 1.1 CR, Hopkins Criteria NPV (see section 11.5), and pathologic CR.

Patients who show signs of clear, clinical progression prior to the treatment end imaging may be considered for surgery. This will be at the discretion of the treating providers, including the surgeon, medical oncologist, and radiation oncologist. Patients who undergo surgery will be determined to have PD in terms of analysis of the primary endpoint.

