13. Patients with residual disease (SD, PR, or PD) on post-treatment imaging will undergo salvage surgical resection (at the discretion of the surgeon) if their disease is felt curable with salvage surgery. Additionally, patients with a CR and clinical suspicion for viable residual disease will be offered salvage surgery. Following pathology analysis, salvage surgical tissue will be sent for correlative studies. Detailed instructions for tissue collection, processing, and shipment are included in the procedures manual.

14. PET imaging at baseline and treatment end is not required for the study, but is allowed for use to determine complete response rate when tumor response on standard imaging cannot confirm CR based on RECIST 1.1. Please see sections 7.1.2.6.2 and 7.1.2.6.3 for details.

15. Screening labs completed within 7 days (168 hours) of treatment initiation (day -7) will not need to be repeated.

16. Once a subject experiences confirmed disease progression or starts a new anti-cancer therapy, the subject moves into the Survival Follow-Up Phase. These subjects will be followed every 6 months to assess for survival status until death, withdrawal of consent, or the end of the study, whichever occurs first.

17. If a subject discontinues pembrolizumab, return visit timing is left to treating physician discretion until day 150 although it is highly recommended that the subject return for Day 78, 120, and 150 so research specimens and QOL can be collected.

18. Minimum interval between pembrolizumab doses is 14 days.

19. Vital signs and weight do not need to occur on the same day as the visit but need to be completed within the window and prior to the next treatment.

20. Once a subject transitions to follow-up all documented AEs will be followed until resolution or to a new baseline as determined by the treating investigator. Only new AEs that could be considered an ECI or irAR will be documented and followed while in follow-up.

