#### 8.4 Analysis Endpoints

#### 8.4.1 **Efficacy Endpoints**

Radiographic Complete response (rCR) rate: proportion of subjects in the analysis population who have a complete response on RECIST 1.1 imaging at treatment end.

PET NPV rate: proportion of subjects in the analysis population who are considered to have NPV based on Hopkins Criteria scoring at treatment end.

Pathologic complete response (pCR) rate: proportion of subjects in the analysis population who have stable disease (SD) or partial response (PR) on RECIST 1.1 imaging at treatment end, who undergo salvage surgical resection and have a complete response determined on histologic evaluation.

Overall Complete Response (CR) rate: this is a composite proportion of subjects in the analysis population with a rCR, PET NPV, and pCR. This is the primary measure of efficacy for the study.

Overall Response Rate (ORR): proportion of subjects in the analysis population who have complete response (CR) or partial response (PR) based on RECIST 1.1 imaging at treatment end.

Progression-Free Survival (PFS): time from Day -7 treatment administration to the first documented disease progression or death.

Overall Survival (OS): time from Day -7 treatment administration to death due to any cause.

Locoregional Control (LRC): time from day -7 treatment to date of local or regional relapse within the primary radiation treatment field (relapse in the head or neck region, excluding CNS recurrence).

Rate of Distant Metastases (DM): proportion of subjects in the analysis population who develop distant recurrence, as defined by recurrence outside of the primary radiation treatment field (head and neck region).

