#### 11.5 Hopkins Criteria for PET Response Evaluation in Head and Neck Cancer

Post-treatment FDG PET/CT imaging will be utilized as part of the response criteria, based on clinical research that showed the utility of this imaging to prevent unnecessary salvage surgery [Mehanna, et al]. PET response will be based on the "Hopkin's criteria."[Marcus et al.]. This is a five point scale with blood pool and liver as reference standard and accommodates FDG uptake due to post radiation inflammation and is outlined below.

Five-Point Qualitative Post-Therapy Assessment Scoring System (Hopkins Criteria) for Head and Neck PET/CT [38]

Score	 F-FDG uptake pattern	Response Category		
1	 F-FDG uptake at the primary site and nodes less than IJV	Complete metabolic response		
2	Focal  F-FDG uptake at the primary site and nodes great than IJV but less than liver	Likely complete metabolic response		
3	Diffuse  F-FDGuptake at the primary site or nodes is greater than IJV or Liver	Likely post-radiation inflammation		
4	Focal  F-FDGuptake at the primary site or nodes greater than liver	Likely residual tumor		
5	Focal and intense  F-FDG uptake at the primary site or nodes	Residual tumor		

**Scores 1, 2, and 3**, which represent complete metabolic response, likely complete metabolic response, and likely post-radiation inflammation, respectively, were considered negative for tumor and have a **Negative Predictive Value (NPV)**.

Scores 4 and 5, which represent likely residual tumor and residual tumor, respectively, were considered positive for tumor and have a **Positive Predictive Value (PPV)**. New lesion would be considered as progressive disease.

Salvage surgery decisions will be left the treatment team and should not be dictated by the PET imaging findings.

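### Section 7.1.2.6.3.4 prints the PET preference in reverse, and it conflicts with section 8.4.1 on whether progression at treatment-end imaging followed by a pathologic CR counts in the primary composite CR (minor)

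*Combined protocol and SAP*

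**What the plan says.** On PET, section 7.1.2.6.3.4 (Salvage Surgery) states: "The preference of the study would be to recommend no further therapy for any PET tumor avidity (CMR", with the bracket closing there. It continues: "However, this is not a requirement and will be left up to the discretion of the treating surgical oncologist". Section 7.1.2.6.3.3 says that patients without a RECIST 1.1 CR whose PET is negative on the Hopkins criteria "can forgo salvage surgery and be considered as having a CR in terms of the primary efficacy measure". Appendix 11.5 gives the scale. Scores 1 to 3 are negative for tumor, and only score 1 carries the label of complete metabolic response. Of scores 4 and 5 it says: "which represent likely residual tumor and residual tumor, respectively, were considered positive for tumor". It adds that PET findings should not dictate the decision on surgery.

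On pathologic response, section 7.1.2.6.3.4 says: "Subjects who have a pathologic CR, but do not have a RECIST 1.1 CR will be included in the final efficacy analysis". Its next sentence describes that analysis as the composite of RECIST CR, Hopkins-negative PET and pathologic CR. Section 8.4.1 defines the pathologic CR rate on subjects "who have stable disease (SD) or partial response (PR) on RECIST 1.1 imaging at treatment end, who undergo salvage surgical resection" with complete response on histology. It then uses that component in the overall CR rate, which it names as the primary measure of efficacy.

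On who reaches surgery, flow-chart footnote 13 (section 6.3) says: "Patients with residual disease (SD, PR, or PD) on post-treatment imaging will undergo salvage surgical resection (at the discretion of the surgeon"), provided the disease is felt to be curable that way. Section 7.1.2.6.3.2 says: "Any patient with documented progression, partial response, or stable disease on post-treatment imaging will undergo salvage surgical procedures to confirm pathologic response".

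**The concern.** There are two separate problems in the text.

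First, the PET sentence taken at its word prefers no further treatment when the PET scan shows tumor uptake. In a curative-intent protocol, the section on salvage surgery is the wrong place for a treatment preference that reads backwards.

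Second, the composite CR is the primary efficacy measure, and its pathologic component has two entry rules. A patient with progressive disease (PD) at treatment-end imaging who then has surgery showing no residual cancer meets the rule of 7.1.2.6.3.4 and fails the rule of 8.4.1. The trial is open-label and the cohorts are small. If the rule is not fixed beforehand, the choice could be made after it is known which reading helps.

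**Working it through.** **PET sentence.** I read CMR as complete metabolic response, the Appendix 11.5 label for score 1; the abbreviation list does not include it. Three texts can be compared with the printed sentence.

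- Its own tag: score 1 is uptake at the primary site and nodes below the jugular vein reference, the lowest category on the scale. That is the absence of avidity.
- Section 7.1.2.6.3.3: PET-negative patients may forgo surgery. Nothing there excuses PET-positive patients from it.
- Appendix 11.5: scores 4 and 5 denote likely or definite residual tumor.

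All three point the same way, and the printed sentence points the other way. The evident meaning is a preference for no further therapy when there is no avidity.

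**Pathologic CR.** The two sections classify patients as follows. Surgery here means salvage surgery after treatment-end imaging with no cancer found on pathology.

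| Situation | Under 7.1.2.6.3.4 | Under 8.4.1 |
|---|---|---|
| RECIST CR | CR | CR |
| SD or PR, then surgery with pathologic CR | CR | CR |
| No RECIST CR, PET Hopkins 1-3 | CR | CR (PET component) |
| PD, no Hopkins 1-3 PET, then surgery with pathologic CR | CR | not CR |
| Surgery before treatment-end imaging | PD | PD (section 8.4.2.2) |

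Only the fourth row differs. The last sentence of 7.1.2.6.3.4, which scores operated patients as PD, does not resolve it. That sentence closes a paragraph on progression before treatment-end imaging, and section 8.4.2.2 gives the same scope.

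The fourth row needs five things together: PD at treatment-end imaging, disease judged curable by surgery, an operation after that imaging, no cancer on pathology, and no Hopkins 1-3 PET. Footnote 13 and section 7.1.2.6.3.2 both name progression among the findings that lead to surgery, so the case is foreseen. The documents give no frequency for it.

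**Size per patient.** Inputs are the cohort sizes (34 HPV+, 23 HPV-) and the cut-offs as printed in section 8.4.7.3 (31 of 34; 18 of 23), assuming full cohorts in the Full Analysis Set. The shift per reclassified patient is 1/n.

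- HPV+: 1/34 = 0.0294, or 2.9 points. Non-CRs allowed at the cut-off: 34 - 31 = 3.
- HPV-: 1/23 = 0.0435, or 4.3 points. Non-CRs allowed at the cut-off: 23 - 18 = 5.

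A cohort's decision would differ between the rules only if its count reaches the cut-off under the broader rule and falls short under the narrower one. With one affected patient, that means exactly 31 against 30 of 34, or exactly 18 against 17 of 23.

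**The case against.** The best reply on PET is that the documents already settle it. The tag shows the intent, 7.1.2.6.3.3 gives the working rule, and both 7.1.2.6.3.4 and Appendix 11.5 leave surgery to the treating team. This stands. A reader might infer that the protocol directs clinicians to leave PET-positive disease untreated; the surrounding text does not support that. What remains is one sentence that says the opposite of what is meant.

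The best reply on pathologic CR is that section 8.4.1 is the endpoint section, so an analyst would follow it, and that 7.1.2.6.3.4 never mentions PD after treatment-end imaging. That is a sensible way to choose, and it is why 8.4.1 is the default below. But the documents state no such precedence. The wording in 7.1.2.6.3.4 covers every patient without a RECIST CR and is tied at once to the composite, so it cannot be read as mere membership of the analysis set.

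It can also be said against 8.4.1 that surgery in documented progression is meant to confirm pathologic response (7.1.2.6.3.2). Under 8.4.1, a PD patient cleared by PET would count as a CR while one cleared by pathology would not. That asymmetry is real. It is a reason for the sponsor to choose deliberately.

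Appendix 11.4, on repeat imaging after a first PD, might be taken as further evidence that the case is expected. It is weak support. It concerns whether to continue treatment, and at treatment-end imaging (about day 150) the last planned pembrolizumab dose (day 141) has normally been given.

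**Conclusion.** Minor, and wrong as written on both counts. The PET preference is reversed; the effect is on clarity of care, not on the analysis. The two sections conflict on one type of patient in the primary endpoint. Few patients, possibly none, will fall there, and each would shift the CR rate by 2.9 points (HPV+) or 4.3 points (HPV-). These are simply one patient's weight in each cohort and do not estimate how often the conflict will arise.

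A reader might infer that the primary result is biased, or that the conflict will decide a cohort. The documents do not support either: they give no rate of PD followed by pathologic CR, and a decision changes only when the count sits at the cut-off. That pathologic CR depends on having surgery is disclosed, including in the Table 7 footnote.

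The conclusion assumes full cohorts of 34 and 23 in the Full Analysis Set and CMR meaning complete metabolic response.

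**What to change.** 1. In section 7.1.2.6.3.4, change the PET sentence so that no further therapy is preferred *in the absence of* any avidity. Keep the CMR tag and the surgeon's discretion. Leave the permission in 7.1.2.6.3.3 for Hopkins 1-3 patients to forgo surgery as it is. Rewriting the preference as Hopkins 1-3 would turn that permission into a recommendation and extend it to score 3, which is diffuse uptake above the reference; the documents do not support that clinical change.
2. State one rule for pathologic CR in both 7.1.2.6.3.4 and 8.4.1 before analysis. The default is the rule of 8.4.1 (SD or PR only). It belongs to the endpoint section and is the more conservative, since it can never give a higher CR count. Report the CR count under the broader rule as a sensitivity result. If the sponsor intends the broader rule, amend 8.4.1 instead.
3. As clerical corrections in the same amendment, bring the unconditional wording on surgery in 4.2.3.1 and 7.1.2.6.3.2 into line with footnote 13, 7.1.2.6.3.3 and 7.1.2.6.3.4. Replace the cross-reference in 7.1.2.6.3.2 to section 7.1.2.7.3.3, which does not exist, with 7.1.2.6.3.4, the section already cited in the footnote to 2.1.

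The cost is one clarification amendment and one extra line in the results. No visit, test or procedure is added.

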#### 7.1.2.7 Tumor Tissue Collection and Correlative Studies Blood Sampling

#### 7.1.2.7.1 Tumor Tissue Collection

All subjects will submit either a "recently obtained" core or excisional biopsy (fine needle aspirate not adequate) to a central lab for characterization of PD -L1 status, performed retrospectively. A "recently obtained" sample may be obtained up to 60 days prior to enrollment. Tissue beyond the 60-day window may be considered with principal investigator approval as long as no intervening systemic therapy has been administered. Subjects for whom recently obtained samples cannot be obtained (e.g. inaccessible or subject safety concern) may submit an archived specimen only upon agreement from the principal investigator. Formalin fixed paraffin embedded (FFPE) are allowable.

# Post-treatment biopsy of the primary site if tumor persists and salvage neck dissection specimens will be analyzed for tumor PD-L1 expression and tumor infiltrating immune cells.

For correlative genomic analysis, an additional portion of the pre-treatment core or excisional biopsy will be used for analysis. If fresh frozen tissue is available, RNA profiling studies may

be performed, but this is not a requirement for the study. Correlative circulating tumor DNA may be also be analyzed. This will be collected in addition to other correlative blood sampling. Details of collection and appropriate specimens are outlined in the procedures manual. Detailed instructions for tissue collection and appropriate specimens are provided in the Procedures Manual.

#### 7.1.2.7.2 Correlative Blood Sampling

Correlative blood sampling for biomarkers of immune response will be collected at key time points during the study. These are not required for all subjects, but are strongly recommended. Timing for correlative blood sampling is outlined in section 6 – Trial Flow Chart. To summarize:

Blood sampling for flow cytometry or functional immune cell analysis will be used to analyze peripheral blood immunocyte populations will occur on day-7, day 15, day 36, day 78, day 120, treatment end (day 150-157), and at 12 months treatment.

#### 7.1.3 Laboratory Procedures/Assessments

Details regarding specific laboratory procedures/assessments to be performed in this trial are provided below. Laboratory tests for hematology, chemistry, urinalysis, and others are specified in Table 5.

Hematology	Chemistry	Urinalysis	Other
Hematocrit	Albumin	Blood	Serum β-human chorionic gonadotropin†
Hemoglobin	Alkaline phosphatase	Glucose	(β-hCG)†
Platelet count	Alanine aminotransferase (ALT)	Protein	Total thriiodothyronine (T3)
WBC (total and differential)	Aspartate aminotransferase (AST)	Specific gravity	Free tyroxine (T4)
Red Blood Cell Count	Lactate dehydrogenase (LDH)	Microscopic exam (If abnormal)	Thyroid stimulating hormone (TSH)
Absolute Neutrophil Count	Carbon Dioxide ‡	results are noted	
Absolute Lymphocyte Count	(CO 2 or bicarbonate)	Urine pregnancy test †	Blood for correlative studies
	Uric Acid		
	Calcium		
	Chloride		
	Glucose		
	Phosphorus		
	Potassium		
	Sodium		
	Magnesium		
	Total Bilirubin		
	Direct Bilirubin (If total bilirubin is elevated above the upper limit of normal)		
	Total protein		
	Blood Urea Nitrogen		
	Creatinine		

#### Table 5 Laboratory Tests

† Perform on women of childbearing potential only. If urine pregnancy results cannot be confirmed as negative, a serum pregnancy test will be required.‡ If considered standard of care in your region.

Screening laboratory tests may be done up to 10 days prior to start of treatment but if done less than 7 days (168 hours) prior to the first dose of treatment on Day -7, they will not need to be repeated. After Day -7, pre-dose laboratory procedures can be conducted up to 72 hours prior to dosing. Results must be reviewed by the investigator or qualified designee and found to be acceptable prior to each dose of trial treatment.

#### 7.1.3.1 **Tissue Collection and Evaluation**

#### 7.1.3.1.1Tumor Collection for p16, PD-L1, and Genomic Analysis

All subjects will have p16 immunohistochemical (IHC) staining (high risk HPV DNA testing may be used as outlined in section 5.1.2) done per institutional standard procedures prior to treatment.

All subjects will submit a recently obtained core or excisional biopsy (within 60 days from enrollment). Fine-needle aspirates (FNAs) are not adequate. Characterization of PD-L1 will be performed using IHC. Detailed instructions for processing of specimens and testing are outlined in the procedures manual and statistical analysis plan (SAP).

For correlative genomic studies, tumor tissue blocks will be micro-dissected and Tumor DNA and RNA will be immediately processed and stored. Detailed instructions for processing of tumor specimens and testing are outlined in the SAP.

For infiltrating immunocyte analysis, tumor tissue blocks will be stored in the Sanford or similar UCSD facility and testing will be completed at a later date. Detailed instructions for processing of tumor specimens are outlined in the SAP.

